## 15.2 Primary efficacy variables

Adverse events will be coded using the most recent version of the Medical Dictionary for Regulatory Activities (MedDRA) coding system to give a System Organ Class (SOC) and Preferred Term (PT) for each adverse event (AE).

Treatment emergent AEs will be defined as AEs with an onset date on or after the date of administration of study drug. If the onset date is missing, the AE will be considered to be treatment emergent. Only treatment-emergent AEs will be summarized. All reported AEs will be listed. The number of AEs, and the number and percentage of patients reporting at least one AE will be summarized by PT nested within SOC for required AE types. AE data will be summarized by dose cohort, and overall.

Microglial activation as measured by [F] FEMPA will be summarised at each time point for each dose cohort and overall as observed value, change from baseline, and % change from baseline. Microglial activation will be summarised with number of observations, mean, median, standard deviation, minimum, maximum, and two-sided 95% CI's.

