#### *6.2.2 Baseline Assessments (Day 1, 2 and 3):*

The activities for the Baseline Assessments will be completed within 30 days of completing the Screening visit. Screening and Day 1 can occur on the same day.

Baseline assessments will include the following activities and will take Day 1-3 to complete, as listed in the schedule of activities. These assessments and subsequent activities will occur as an inpatient of Macquarie University Hospital. All assessments listed below must be completed prior to enrollment of the subject into the treatment phase of the study.

- Review of continuing ability to consent
- Vital signs (blood pressure, heart rate and temperature), height and weight
- Physical examination
- ECG

- Blood collection for clinical laboratory assessments (daily)
- Urinalysis (day 3)
- Blood and urine collection for research samples (daily)
- Urine pregnancy test (Day 1)
- Neurological exam (incl. ALSFRS-R and UMN Index)
- Brain MRI (Day 2)
- Brain PET Imaging (Day 2)
- Lumbar puncture for collection of CSF (Day 3)
- Review of concomitant medications
- Review of current medical conditions
- Review of adverse events related to lumbar puncture
- Repeat review of the inclusion/exclusion criteria

Once all Visit 1 activities have been completed and the Investigator determines that all eligibility criteria have been met, the subject may be enrolled into the study. Once enrolled, the subject will be enrolled in one of two dose levels of 3K3A-APC (15mg or 30mg).

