### 10.1 Adverse Event Definitions

#### Adverse Events (AE)

An AE is any undesirable experience occurring to a subject during a clinical trial, whether or not considered related to the investigational product.

Pre-existing conditions (i.e., undesirable experiences, signs or symptoms that begin prior to the Screening Visit) will be recorded on the medical history CRF page. These conditions will not be reported as an AE unless they worsen in intensity or frequency after the Screening Visit.

Treatment-emergent AEs are undesirable experiences, signs, or symptoms that begin or worsen in intensity or frequency at the time of or after the administration of study drug.

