#### 10.4 Recording of Adverse Events

Adverse events including clinically significant biological sample test abnormalities, whether observed by the investigator, elicited from or volunteered by the subject, should be recorded on the Adverse Event Log. This will include a brief description of the experience, the date of onset, the date of resolution, the severity, and seriousness and whether the event was related to participation in the research study.

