## 15.6 Physical and Neurological Examinations

A physical examination and neurological examinations will be performed at times stipulated in the Protocol Schedule of Assessments. Physical examination and neurological findings will be listed by Visit and Participant. Clinically significant changes will be captured as adverse events.

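### Sections 10.1 and 15.2 define treatment-emergent AEs differently, so the primary safety tables depend on which definition is applied

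*Combined protocol and SAP*

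**What the plan says.** Safety is part of the primary outcome, and AEs are analysed in section 15.2. That section, with the same wording in the synopsis under Statistical Methods, states: "Treatment emergent AEs will be defined as AEs with an onset date on or after the date of administration of study drug". An AE with no onset date is treated as treatment-emergent. The consequence of the label is set out next: "Only treatment-emergent AEs will be summarized. All reported AEs will be listed". The tables are then specified: "The number of AEs, and the number and percentage of patients reporting at least one AE will be summarized by PT nested within SOC".

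Section 10.1 has its own definition: "Treatment-emergent AEs are undesirable experiences, signs, or symptoms that begin or worsen in intensity or frequency at the time of or after the administration". The reference point there is the giving of study drug. For conditions that pre-date screening it adds: "These conditions will not be reported as an AE unless they worsen in intensity or frequency after the Screening Visit".

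Three other places bear on how the definitions work in practice:

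- Section 6.2.2 lists among the baseline assessments "Lumbar puncture for collection of CSF (Day 3"), together with a review of puncture-related AEs. It requires these assessments to be finished before the treatment phase. Sections 6.2.3 and 8.2 start dosing on Day 3 as well.
- Section 10.4 describes the AE log: "This will include a brief description of the experience, the date of onset, the date of resolution, the severity, and seriousness", followed by relatedness. No onset time is named.
- Section 15.6 says of examination findings: "Clinically significant changes will be captured as adverse events".

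**The concern.** The two definitions differ on two axes. Section 10.1 works from the moment of administration; 15.2 works from the calendar date. Section 10.1 counts worsening; 15.2 counts only onset. Nothing in the documents says which one governs.

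This matters because the label decides what enters the only AE tables the plan describes. The trial is open-label and uncontrolled, so no comparator shows how many events come from procedures alone, and section 4 intends the results to guide dosing in chronic studies. If the choice is left until the tables are programmed, it can be made with the data in view, and either choice would have support in the protocol.

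**Working it through.** There is no stated figure to reproduce. The check applies both rules to the possible event histories and then shows the scale of one reclassified patient.

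**Step 1: timing.** Dose 1 is on Day 3 (6.2.3, 8.2), and so is the baseline puncture (6.2.2). Five doses 12 hours apart span 4 × 12 = 48 hours, so a Day 3 to Day 5 course fits almost any clock time for dose 1. The schedule gives no clock times, so the gap between puncture and dose 1 is not bounded. The puncture-first order is strongly implied but not fully settled, because 6.2.2 also ties enrolment to completing the Visit 1 activities.

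**Step 2: classification.**

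| Event history | 10.1 | 15.2 |
|---|---|---|
| Starts Day 1, never worsens | No | No |
| Starts Day 2, worsens after dosing | Yes | No if the original onset date is kept; Yes if the worsening is logged as a new AE |
| Starts Day 3 before dose 1, never worsens | No | Yes |
| Starts Day 3 before dose 1, worsens after dosing | Yes | Yes |
| Starts Day 3 after dose 1 | Yes | Yes |

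The rules disagree on the third row and, depending on how worsening is recorded, on the second. The third row makes the 15.2 tables larger and the second can make them smaller, so the net direction cannot be derived.

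**Step 3: can the log settle it?** The fields listed in 10.4 give an onset date but no time and no date of worsening. From those fields alone, 10.1 cannot be applied to Day 3 events. Sections 10.1 and 15.6 make worsened pre-existing conditions and significant examination changes reportable, but neither says which onset date they carry.

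**Step 4: exposure window for the second row.** Section 6.2.2 allows screening on Day 1, which is 3 − 1 = 2 days before dose 1. It also allows up to 30 days from screening to completion of baseline (Days 1-3), so screening can be about 30 days before dose 1. This window covers AEs that first arise after screening. A condition that pre-dates screening could carry a still earlier date, since no dating rule is given.

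**Step 5: scale.** Section 2 caps each cohort at 8, so 16 overall. Section 15.1 specifies Clopper-Pearson intervals. The lower limit is the 0.025 quantile of Beta(x, n−x+1), or 0 when x = 0. The upper limit is the 0.975 quantile of Beta(x+1, n−x).

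| x/n | Rate | 95% CI |
|---|---|---|
| 0/8 | 0% | 0-36.9% |
| 1/8 | 12.5% | 0.3-52.7% |
| 0/16 | 0% | 0-20.6% |
| 1/16 | 6.25% | 0.2-30.2% |

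One patient with no other counted event of that preferred term therefore moves a cohort rate by 1/8 = 12.5 points and the overall rate by 1/16 = 6.25 points, up or down. The intervals overlap widely. The tabulated number of AEs changes by 1 for each discrepant event, even when the patient count does not move.

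**The case against.** The strongest reply is that the mismatch is real but light. The study is descriptive, with at most 16 patients. All AEs are listed, relatedness is graded (10.2), serious events are reported within 24 hours whatever their label (10.5), and no decision rule uses the treatment-emergent count. The Day 3 route is narrow: a puncture headache that starts after dose 1 counts under both rules, and section 12.2 gives no onset times for puncture risks. With dates only, the rule in 15.2 is a workable, conservative way to apply 10.1. Pre-dose status might be recovered from inpatient source notes, and a dating rule could sit in the operation manuals that section 13.1 mentions. The shift from 0/8 to 1/8 is what any single patient does at n = 8 and says nothing about frequency.

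Most of this stands as a limit on size. It does not remove the contradiction. The date rule may be a conservative approximation for Day 3 onsets, but it is not conservative for earlier AEs that worsen, which it can leave out. The listing lets a careful reader rebuild the counts only if time and worsening were recorded, and 10.4 requires neither. Relatedness grades do not repair the tables, because 15.2 does not name a table by relatedness.

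**Conclusion.** The concern holds and should be fixed before the safety tables are produced. Two current definitions of the same term classify some AEs differently: a Day 3 pre-dose AE that does not worsen counts only under 15.2, and an AE from before Day 3 that worsens after dosing is sure to count only under 10.1. Loss of the latter from the 15.2 tables is possible, not certain.

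Confidence is high for the mismatch itself. Its practical effect is unknown, because the documents give no event rate and no interval between puncture and dose, and none is assumed here. The figures for one patient assume full cohorts of 8 and no other counted event of the same preferred term in that patient. The effect is confined to the descriptive primary safety tables.

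**What to change.** Put one definition in 10.1, 15.2 and the synopsis: an AE is treatment-emergent if it starts, or becomes more intense or more frequent, at or after the start of the first infusion. Then:

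- Record an onset time for AEs that start on Day 3.
- Keep the conservative default: a missing onset date, or a missing time for a Day 3 onset, counts as treatment-emergent.
- State one rule for dating post-dose worsening so that it reaches the tables. A new AE entry dated at the worsening is one convention among several.

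The cost is one harmonised sentence in three places, one dating rule, and one eCRF time field if it does not already exist. The downside is slightly more AE entries. If worsening opens a new entry, one episode can add 2 to the number of AEs, so the table should say how such pairs are counted. No extra visits or patients are needed.

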#### 7.1.6 Adverse Events

During each visit participants will be asked about adverse events. AEs will be recorded on an ongoing adverse event log.

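### The missing-onset rule in Section 15.2 counts an AE as treatment-emergent even when its resolution date falls before the first infusion (minor)

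*Combined protocol and SAP*

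**What the plan says.** Section 15.2 of the combined protocol and SAP sets the main rule by calendar date: "Treatment emergent AEs will be defined as AEs with an onset date on or after the date of administration of study drug". It then deals with absent dates: "If the onset date is missing, the AE will be considered to be treatment emergent". The Statistical Methods entry of the synopsis repeats both. Neither place qualifies the second sentence, and no other section supplies an exception.

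The flag decides what is tabulated: "Only treatment-emergent AEs will be summarized. All reported AEs will be listed".

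Section 10.1 defines the same term by what happened to the patient. The event must "begin or worsen in intensity or frequency at the time of or after the administration of study drug".

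Section 10.4 lists what the AE log holds, including "the date of onset, the date of resolution, the severity, and seriousness". Section 7.1.6 adds that "During each visit participants will be asked about adverse events", so events can be logged before dosing. Sections 6.2.3 and 8.2 put the first infusion on Day 3. Section 6.2.2 allows up to 30 days between Screening and baseline, or both on the same day.

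**The concern.** Counting an event of unknown onset as treatment-emergent is a sound default while its timing is unknown. The sentence in 15.2 goes further. It also applies when another field on the same log settles the timing. An event that resolved before Day 3 neither began nor worsened at or after dosing, so 10.1 excludes it and 15.2 includes it.

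Reconciling the other difference between the two definitions, worsening, would not cure this. The missing-date sentence operates whatever the date comparison says.

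At stake is the accuracy of the AE tables for the primary outcome. The trial is uncontrolled, so no comparator row would carry the same error. With at most 8 patients per cohort, a single record changes the displayed percentage visibly.

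**Working it through.** The plan gives no figure to reproduce here. The check is to apply the rule as written to possible records, then size the effect of one of them.

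**Inputs.** First infusion on Day 3 (6.2.3, 8.2). Resolution date on the log (10.4). At most 8 patients per cohort (Section 2), 16 in total (synopsis). Exact Clopper-Pearson two-sided 95% intervals for categorical parameters (15.1, synopsis).

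**Step 1: classification.** The last column adds one exception: a missing onset is not treatment-emergent if resolution is before Day 3.

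| Record | 15.2 as written | With resolution-date exception |
|---|---|---|
| Onset Day 2, resolved Day 2 | No | No |
| Onset Day 4, resolved Day 5 | Yes | Yes |
| Onset missing, resolved Day 2 | **Yes** | **No** |
| Onset missing, resolved Day 3 | Yes | Yes |
| Onset missing, resolved Day 6 | Yes | Yes |
| Onset and resolution missing | Yes | Yes |

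One of the six patterns changes. The first and third rows may describe the same event. Only the blank onset field makes 15.2 treat them differently.

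**Step 2: effect of one such patient**, assuming no other patient has that Preferred Term.

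- For 0/n, the upper limit is 1 − 0.025^(1/n). With n = 8 this is 1 − 0.631 = 36.9%. With n = 16 it is 1 − 0.794 = 20.6%.
- For 1/n, the lower limit is 1 − 0.975^(1/n), which is 0.3% for n = 8 and 0.2% for n = 16.
- For 1/n, the upper limit p solves (1 − p)^n + n·p·(1 − p)^(n−1) = 0.025, which gives 52.7% for n = 8 and 30.2% for n = 16.

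| Row | Without the record | With the record | Shift |
|---|---|---|---|
| One cohort | 0/8 = 0% (0 to 36.9%) | 1/8 = 12.5% (0.3 to 52.7%) | 12.5 points |
| Overall | 0/16 = 0% (0 to 20.6%) | 1/16 = 6.25% (0.2 to 30.2%) | 6.25 points |

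**Step 3: frequency.** This cannot be computed. The documents give neither a rate of pre-dose AEs nor a rate of missing onset dates.

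**The case against.** Four arguments weigh against the point.

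- **The default is conservative.** It can over-count events but cannot conceal one, and every AE is listed, so a reader could find the record. This stands and limits the severity. It does not justify the rule for an event already shown to have ended before dosing, because no uncertainty is left to be conservative about.
- **Missing onset dates should be rare.** Section 10.4 calls for the date, Section 16 provides real-time queries resolved before lock, Section 17 requires monitoring of completeness, and inpatients are assessed daily. This stands. The most plausible source is an event recalled from the outpatient interval between Screening and admission.
- **No decision depends on it.** The analyses are descriptive, and no AE threshold or escalation rule is tied to these counts. This stands.
- **Not every early record is misclassified.** A reader might infer that any event first reported at Screening, Visit 1 or Visit 2 is also wrongly counted. The documents do not support that. Section 10.4 lists no first-report visit among the log's contents. Section 10.1 sends conditions that began before Screening to medical history unless they worsen. An unresolved event logged on Day 1 or 2 may still worsen after dosing, and 10.1 would then count it.

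**Conclusion.** The point holds for one kind of record: onset date missing and resolution date before the first infusion. For it, 15.2 and the synopsis give a classification that 10.1 contradicts, and the event enters the primary safety tables. Each such patient adds up to 12.5 percentage points to a cohort row and 6.25 to the overall row. These figures illustrate one patient and do not predict how many there will be.

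A reader might go further and infer that many events will be misassigned, or that the 15 mg and 30 mg tables will be distorted differently. The documents give no rate from which to estimate the first and nothing that shows the second.

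Severity is minor: the case is probably rare, the error overstates events and hides none, and no stated decision turns on it. The conclusion assumes that the resolution date on the log is correct.

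**What to change.** Replace the missing-date sentence in Section 15.2 and in the synopsis with, for example:

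> *An AE with no onset date is classed as treatment-emergent unless its resolution date is before the date of the first infusion. An AE with a partial onset date is classed as treatment-emergent unless the known part shows that it began before the first infusion and it did not worsen after dosing. Where these fields do not settle the timing, the AE is treatment-emergent. Every AE remains in the listing.*

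This keeps the conservative default wherever timing is truly unknown and agrees with 10.1. The cost is a short change in two places and one condition in the AE program. The main limb uses a date the log already holds. The partial-date limb also needs evidence that the event did not worsen. The contents listed in 10.4 include no date of worsening, so without such evidence the event should stay treatment-emergent. The small downside is that the flag now depends on the resolution date being right. A wrong date could move an event out of the tables, but it would still appear in the listing.

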### 7.2.2 Microglial PET Imaging

Subjects will undergo [F] FEMPA PET imaging to assess the activation state of microglia in the brain. On Day 2 and Day 9 subjects will receive approximately 200 MBq of [F] FEMPA with dynamic brain scanning from time=0 to 50 minutes according to previously established protocols. Scanning time will be 50 minutes in total.

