### 7.2.3 Brain MRI (ALS protocol)

Subjects will undergo a structural MRI brain scan on Day 2 and on Day 9 according to established protocols (9). At the discretion of the investigator and imaging staff, subjects who have presence of pacemakers, aneurysm clips, artificial heart valves, cochlear implants, metal fragments or foreign objects in the eyes, skin or body or any other known contra-indication to MRI may be advised not to complete a baseline (or follow-up) MRI scan, but these subjects may still participate in the study. MRI is being conducted to assess the structure of the brain, for co-registration with PET images as well as assessing the integrity of the blood brain barrier.

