### 8.2 Study medication administration

The study medication must be infused within 8 hours of preparation.

The 100mL of study medication will be administered by IV infusion over 15 minutes (by pump set to 400mL/hr). Five doses of study medication will be administered at 12 hourly intervals  $\pm$  1 hour starting on day 3 of hospitalization and finishing on day 5 of hospitalisation. Study drug should be flushed from infusion line with 0.9% sodium chloride.

If a hypersensitivity reaction develops, infusion is stopped immediately and no further doses of study medication will be administered.

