### 12.5 Unknown Risks

In addition to the known risks listed above, the imaging procedures in this study may cause unknown risks to the participant, or a developing embryo or fetus or possible risks to the future offspring of male participants. Female subjects or a female partner of a male subject who report a pregnancy within 30 days of [F]FEMPA injection will be asked to have a urine pregnancy test.

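### Section 15.2 tabulates only treatment-emergent AEs, so AEs before dosing, including reactions to the Day 2 PET/MRI session, are only listed and this uncontrolled trial has no tabulated within-subject AE reference

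*Combined protocol and SAP*

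**What the plan says.** Section 15.2, repeated in the synopsis under Statistical Methods, sets the AE reporting rule: "Only treatment-emergent AEs will be summarized. All reported AEs will be listed". The classification goes by date: "Treatment emergent AEs will be defined as AEs with an onset date on or after the date of administration of study drug". Undated events are put on the treatment side: "If the onset date is missing, the AE will be considered to be treatment emergent".

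Section 10.1 defines the same term differently, as events "that begin or worsen in intensity or frequency at the time of or after the administration of study drug". It has a worsening clause that 15.2 lacks.

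The imaging session takes place twice. Section 7.2.2: "On Day 2 and Day 9 subjects will receive approximately 200 MBq of" the FEMPA tracer. Section 7.2.3: "Subjects will undergo a structural MRI brain scan on Day 2 and on Day 9". The five infusions lie between the two sessions, "starting on day 3 of hospitalization and finishing on day 5 of hospitalisation" (8.2). Lumbar punctures are on Days 3 and 10 (Schedule of Activities, 7.2.5). The first is among the baseline assessments that 6.2.2 requires before the treatment phase.

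AEs are asked about at each visit (7.1.6) and graded for relationship to study drug on five levels (10.2). Section 15 plans no AE summary by study period, procedure or relationship. On imaging risk, 12.5 says that "the imaging procedures in this study may cause unknown risks to the participant", and 12.4 refers to a companion protocol that is not among the documents.

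**The concern.** Restricting AE tables to treatment-emergent events is ordinary where a control arm supplies the background rate. Section 2 describes this trial as open label and uncontrolled. The only AE reference from the same people, on the same ward and undergoing the same imaging, is the short inpatient period before the first infusion. The plan collects those events but does not tabulate them. For laboratory values, vital signs and PET it does present the pre-dose state and the change from it.

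A reader of the treatment-emergent table will see headaches, line-site complaints and other events of a hospital stay with repeated procedures. No table will show how often the same events occurred in the same subjects before any study drug. What is at stake is how well the primary safety table can be interpreted.

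**Working it through.** The plan gives no AE rate, power or sample-size figure, so there is nothing of its own to reproduce.

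**Step 1. Apply the 15.2 date rule to the procedure days.** The first dose is on Day 3 (6.2.3, 8.2). A reaction that starts on the day of the procedure is treatment-emergent if that day is 3 or later.

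| Procedure | Day | In the AE table? |
|---|---|---|
| PET/MRI, first | 2 | No, listed only |
| Lumbar puncture, first (baseline) | 3 | Yes |
| PET/MRI, second | 9 | Yes |
| Lumbar puncture, second | 10 | Yes |

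The imaging asymmetry follows directly. So does a second effect: the rule uses the date alone, so a reaction to the Day 3 puncture counts as treatment-emergent even if it began before the first infusion.

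**Step 2. Exposures.** With full attendance there are 16 × 2 = 32 tracer injections, of which 16 precede dosing. The MRI count is the same at most, because 7.2.3 lets subjects with contraindications go without the scan.

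**Step 3. Observation time.** Elapsed days are counted to Day 3 and from Day 3 to Day 15.

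- Post-dose: 12 × 16 = 192 patient-days.
- Pre-dose minimum (Screening on Day 1, allowed by 6.2.2): 2 × 16 = 32, which is 32/224 = 14% of the total.
- Pre-dose maximum: (30 + 2) × 16 = 512, or 512/704 = 73%, if Screening is 30 days before Day 1. If all baseline work through Day 3 must fall within 30 days of Screening, it is 30 × 16 = 480, or 480/672 = 71%.

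These shares measure observation time, not bias. Everything above 32 patient-days is recall between Screening and admission and says nothing about imaging reactions.

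**Step 4. Possible size in the tables.** The documents give no reaction rate. Assume a per-session risk p, equal and independent at the two sessions, with no drug effect, and let p run from 2% to 20%. The expected reactions in 16 subjects are 16p per session and 32p for both. The chance of at least one Day 9 reaction in a cohort of 8 is 1 − (1 − p)^8.

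| p | Tabulated as planned (Day 9 only) | Tabulated with a pre-dose table (both) | Chance of at least one Day 9 reaction, n = 8 |
|---|---|---|---|
| 2% | 0.32 | 0.64 | 15% |
| 5% | 0.80 | 1.60 | 34% |
| 10% | 1.60 | 3.20 | 57% |
| 20% | 3.20 | 6.40 | 83% |

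One such subject moves a cohort from 0/8 (exact 95% CI 0% to 36.9%) to 1/8 (0.3% to 52.7%). As a further assumed example, take 3 of 16 subjects with headache after each session. The planned table shows 3/16 = 19% (4% to 46%), and the matching 3/16 from before the drug can be found only in the listing.

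**Step 5. The two definitions.** A Day 2 event that worsens after dosing is treatment-emergent under 10.1 but not under 15.2. A Day 2 event with no recorded date is treatment-emergent under 15.2.

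**The case against.** The strongest reply is that nothing is lost. Every AE is listed, there are at most 16 subjects, the analysis is descriptive, and anyone can count the Day 2 events. Tabulating treatment-emergent AEs and listing the rest is a coherent plan. Much of this stands, and it is why the point is minor. But a listing gives no denominators or rates by cohort, and the wording in 15.2 excludes a pre-dose table; it does not leave the matter open.

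Three stronger readings are tempting, and the documents do not support them.

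- **Day 2 reactions are left out of every summary.** This is true of AE summaries only, and only for a recorded onset before Day 3. Vital signs and safety laboratory values are summarised at every scheduled time point (15.4, 15.5), and the schedule has both on Day 2. A delayed reaction that starts on Day 3 or later is tabulated.
- **Day 9 reactions are counted against 3K3A-APC.** Treatment-emergent is a timing label. Section 10.2 allows a scan reaction to be graded unrelated or unlikely. What can fairly be said is that no table by relationship is promised. The phrase about required AE types in 15.2 is undefined and neither promises nor excludes one.
- **The treatment-emergent table is biased.** It reports what it defines. Leaving out pre-dose events does not distort it; it only leaves it without a comparator.

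The tracer argument should also be kept modest. The statement in 12.5 is generic, and FEMPA safety may be handled in the companion protocol, which cannot be checked here.

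**Conclusion.** The point holds as a gap in presentation. AEs with a recorded onset before Day 3 are only listed, while the same events after Day 9 imaging enter their dose cohort's table without a planned split by relationship to drug or procedure. One of the two imaging sessions, 16 of 32 tracer injections with full attendance, is outside the AE tables. Safety is the primary outcome and there is no control group, so a pre-dose table would make the main result easier to read.

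It is an inexpensive improvement. The reference it supplies is small: 32 inpatient patient-days, and even 0/16 has an exact upper limit of 20.6%. It would give context and would not support a formal comparison. The reaction rates used above are assumptions. The conclusion also assumes that AEs of every kind are asked about on Days 1 to 3, as 7.1.6 implies; the list in 6.2.2 names only those related to lumbar puncture.

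**What to change.** In 15.2 and the synopsis:

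1. Keep the treatment-emergent table. Add a table of pre-dose AEs in the same SOC/PT layout, by cohort and overall, with patient-days. Show the inpatient part (Day 1 to first infusion) separately from the recalled interval between Screening and admission.
2. Record the onset time of Day 3 AEs and classify them against the start of the first infusion. Otherwise pre-infusion puncture reactions are counted as treatment-emergent, or fall in both tables.
3. Reconcile 10.1 (begin or worsen) with 15.2 (onset date only), so that one definition governs.
4. If the two imaging sessions are compared in the same subjects, end both windows at the next lumbar puncture: Day 2 imaging to the Day 3 puncture, and Day 9 imaging to the Day 10 puncture. Ending the first window at the infusion would include a puncture that the second leaves out. Section 12.2 names headache and site pain as the commonest puncture risks, so that would inflate the pre-drug side.
5. State in 6.2.2 that all AEs are asked about on Days 1 to 3.

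The cost is a few lines of text, one or two tables and one new item on the AE log. Section 10.4 records only the date of onset, so the Day 3 time is not yet collected.
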